6.7. Criteria for Permanent Discontinuation of Study Treatment

A patient may choose to withdraw from study treatment at any time or be withdrawn from study treatment by the Investigator or Sponsor, if the patient does not comply with study requirements. If a patient is withdrawn from any/all study treatment, reasonable efforts will be made to determine the reason for withdrawal, and this information will be recorded in the eCRF.

As of IRB/IEC approval of Amendment 3, patients who request to discontinue receipt of study treatment will remain in the study and must continue to be followed for protocolspecified follow-up procedures (see Section 7.1.4.2 and Section 7.1.4.3). The only exception to this is when a patient specifically withdraws consent for any further contact with him or her or persons previously authorized by the patient to provide this information. Patients should notify the investigator in writing of the decision to withdraw consent from future follow-up, whenever possible. The withdrawal of consent should be explained in detail in the medical records by the investigator, as to whether the withdrawal is only from further receipt of study treatment or also from study procedures and/or posttreatment study followup, and entered on the appropriate CRF page. In the event that vital status (whether the patient is alive or dead) is being measured, publicly available information should be used to determine vital status only as appropriately directed in accordance with local law.

Patients meeting any of the following criteria **must** discontinue all study treatment:

• Withdrawal of consent. Patients may choose to withdraw from the study at any time without penalty of jeopardizing their healthcare or loss of benefits to which the patient is otherwise entitled. Patients will have the option of withdrawing consent for study treatment but continue in the follow-up period of the study for safety/efficacy assessments.

Note: Consent withdrawn **from study treatment** means that the patient may choose to discontinue study treatment but remain in the study to be followed for safety, progression, subsequent therapies and survival. In this case, follow-up data will continue to be collected for this patient.

Note: Consent withdrawn for the **study** means that the patient has explicitly indicated that they do not want to be followed any longer; in this case no further data, except data in the public domain, may be solicited from or collected on the patient.

- Unacceptable AEs or failure to tolerate study treatment is defined as:
 - Grade 4 or life-threatening AE as outlined in Appendix 2 and Appendix 3, (except with approval from the Sponsor);
 - Toxicity requiring more than the allowed number of dose reductions for encorafenib and binimetinib as described in Table 7 and Table 8, respectively;
 - Occurrence of an AE that is related to study treatment and in the judgment of the Investigator compromises the patient's ability to continue study-specific procedures, or is considered to not be in the patient's best interest.
- Patient has missed > 6 weeks (i.e., 42 consecutive days) of dosing per Section 6.6.1.
- Disease progression per RECIST v1.1.
- Clinical progression, as determined by the Investigator in the absence of radiographic progression.
- Patient becomes pregnant or begins breastfeeding.
- Significant protocol deviation that, in the opinion of the Investigator and/or Sponsor, renders the patient unsuitable for further study treatment administration.
- Patient is noncompliant with study procedures or study treatment that in the judgment of the Investigator or Sponsor renders the patient unsuitable for further study participation.
- Patient is lost to follow-up.
- Death.
- Termination of the study by the Sponsor (described in Section 4.6 and Section 9.10). Version 5 Pfizer Confidential

If the decision is made to permanently discontinue study treatment the EOT visit should be conducted (see Section 7.1.3). Reasonable efforts should be made to have the patient return for all applicable follow-up visits (safety and efficacy), as outlined in the Table 3. The date of the last dose of study treatment will be recorded in the eCRF.

6.8. Criteria for Study Discontinuation

Patients will be considered as having discontinued the study if any of the following criteria are met:

- Patient completes all required follow-up visits.
- Patient dies, and the date of death is available or patient is known to have died; however, the date of death cannot be obtained. *Note:* Every effort must be made to obtain the date of death.
- Consent is withdrawn for any further contact related to the study. *Note:* Every reasonable effort should be made to determine the reason a patient withdraws prematurely, and this information should be documented in the eCRF.
- Patient is lost to follow-up.
- Termination of the study by the Sponsor (described in Section 4.6 and Section 9.10).
- Termination of the study by the local health authority, IRB or IEC.

6.9. Intervention after the End of the Study

At the end of the study, all patients who have otherwise not met the protocol-defined criteria for treatment withdrawal (see Section 6.7), will be offered access to study treatment in accordance with applicable regulations and requirements (i.e., including where required, separate health authority approval for continued access).

6.10. Enrollment of Additional Patients

Additional patients may be enrolled to ensure that there are at least 60 treatment-naïve patients and 37 previously treated patients whose tumors have locally confirmed $BRAF^{V600E}$ mutation, and who have received at least one dose of study treatment. Up to 10 additional patients who have a $BRAF^{V600}$ mutation other than $BRAF^{V600E}$ ($BRAF^{V600x}$) can be enrolled and treated. It is not expected that more than 107 patients with any $BRAF^{V600}$ mutation will be enrolled and treated.

6.11. Lost to Follow up

A patient will be considered lost to follow-up if he or she repeatedly fails to return for scheduled visits and is unable to be contacted by the study site.

The following actions must be taken if a patient fails to return to the study site for a required study visit:

- The site must attempt to contact the patient and reschedule the missed visit as soon as possible and counsel the patient on the importance of maintaining the assigned visit schedule and ascertain whether the patient wishes to and/or should continue in the study.
- Before a patient is deemed lost to follow-up, the Investigator or designee must make every effort to regain contact with the patient. These contact attempts will be documented in the patient's medical record.
- Should the patient continue to be unreachable, he/she will be considered to have withdrawn from the study and lost to follow-up.

7. STUDY VISITS AND ASSESSMENTS

The timing of study visits and assessments are summarized in the SoA (Table 3). Protocol waivers or exemptions are not allowed. Safety concerns should be discussed with the Sponsor immediately upon occurrence or awareness to determine if the patient should continue or discontinue study treatment. Adherence to the study design requirements, including those specified in the SoA, is essential and required for study conduct.

7.1. Study Visits

7.1.1. Screening

Screening is the interval between signing the ICF up to the time at which the patient receives the first dose of study treatment (i.e., Cycle 1 Day 1). Screening may not exceed 28 days. Assessments that are required to demonstrate eligibility may be performed over the course of 1 or more days during the Screening process.

Procedures conducted as part of the patient's routine clinical management (e.g., blood count, imaging study) and obtained before signing of the ICF may be utilized for Screening or baseline purposes provided the procedures met the protocol-specified criteria and were performed within the time frame defined in the SoA (Table 3). If baseline scans from an institution other than the investigational site are used, the site must obtain copies of the scans prior to enrollment of the patient, or the scans must be repeated at the investigational site and submitted for independent review (see Section 7.2.4).

All Screening evaluations must be completed and reviewed to confirm that potential patients meet all eligibility criteria. The Investigator will maintain a screening log to record details of all patients screened and to confirm eligibility or record reasons for screening failure, as applicable. Tests with results that fail eligibility requirements may be repeated once during screening if the Investigator believes the results to be in error. For screening assessments that are repeated, the most recent available results before first dose of study treatment will be used to determine eligibility.

See Section 5.4 and Section 6.10 for information regarding screen failures and enrollment of additional patients, respectively.

7.1.1.1. BRAF^{V600} Mutation Testing

Patients will be eligible for the study based on identification of a $BRAF^{V600}$ mutation in the tumor tissue or blood (e.g., ctDNA genetic testing), as determined by a local laboratory assay. Patients must have written documentation from a previous local pathology report of $BRAF^{V600}$ mutation in tumor tissue or by genetic blood test. Only PCR and NGS-based local assay results will be acceptable for tumor tissue or blood.

The Investigator must confirm prior to enrollment that the patient has adequate tumor tissue available for confirmation of $BRAF^{V600}$ mutation status by the central laboratory. Results of central confirmation of $BRAF^{V600}$ mutation status is not required prior to enrollment and will not be used for determining patient eligibility.

Archived tumor tissue or a newly obtained core or excisional biopsy sample from all patients are required to be submitted to the central testing laboratory. FNA is acceptable provided there is sufficient material (1 block or a minimum of 8 unstained slides [up to 15 unstained slides is preferred]) from the same sample used to obtain the local BRAF positive result available to send to the central laboratory.

For archival tumor tissue samples, whenever possible the sample sent for central testing should be from the same tumor block that was used for local $BRAF^{V600}$ mutation testing. A minimum of 8 slides (up to 15 is preferred) should be submitted to the central laboratory to ensure adequate sample for testing. Tumor cells from pleural fluid are permitted provided the sample has been centrifuged to generate a formalin-fixed, paraffin-embedded block with sufficient tumor nuclei (i.e. >20% tumor nuclei). Liquid samples are not permitted. One block or a minimum of 8 unstained slides (up to 15 unstained slides is preferred) must be sent to the central laboratory. Further details regarding sample submission including instructions for sample preparation and shipping will be provided in the Laboratory Manual.

If a fresh biopsy is taken, the biopsy should be taken from a nontarget lesion when possible.

7.1.2. Treatment Period

The treatment period begins on the day the patient receives the first dose of study treatment (i.e., Cycle 1 Day 1) through the point which the patient permanently discontinues all study treatment. During the treatment period, patients will have regularly scheduled assessments as outlined in the SoA (Table 3).

7.1.3. End of Treatment and/or Early Termination

When the patient permanently discontinues all study treatment (see Section 6.7), whether the patient is terminating the study early or has completed the study (see Section 6.8), the EOT visit should be conducted. If the EOT visit coincides with a regular study visit, the EOT evaluations will supersede those of the scheduled visit, and the data will be entered in the EOT visit in the eCRF.

If the patient is withdrawn from study treatment and/or study:

- The study monitor and Sponsor must be notified.
- The primary reason for withdrawal must be documented in the patient's medical record and in the eCRF. *Note:* The reason for withdrawal from treatment may be different from the reason for withdrawal from study. For example, patients can discontinue treatment for disease progression or toxicity, but remain in the study for safety and survival follow-up.
- The EOT and safety follow-up visits as outlined in the SoA (Table 3) should be performed.
- Patients should be followed for safety as outlined in Sections 7.1.4.1 and 7.5.1.1.
- Patients who discontinue study treatment for reasons other than disease progression will continue to be followed for disease status as outlined in Section 7.1.4.2.
- All patients who discontinue study treatment will continue to be followed for subsequent anticancer therapies and survival (see Section 7.1.4.3).
- If the patient withdraws consent for disclosure of future information, the Sponsor may retain and continue to use any data collected before such a withdrawal of consent.
- If a patient withdraws from the study, he/she may request destruction of any samples taken and not tested, and the Investigator must document this in the site study records.

7.1.4. Post-treatment Follow-up

Cutaneous squamous cell carcinoma has been observed in patients treated with BRAF inhibitors including encorafenib. It is recommended that dermatologic screening for skin malignancies be performed every 8 weeks until 6 months after the last dose of encorafenib. Patients should be instructed to immediately inform the Investigator if new skin lesions develop.

7.1.4.1. 30-Day Safety Follow-up

The safety follow-up period is the interval between the EOT visit and the scheduled followup visit, which should occur 30 days (+ 7 days) after the EOT visit (or after the last dose of study treatment if the EOT was not performed). Adverse events and SAEs must be reported as outlined in Section 7.5.1.1 and Section 7.5.1.2. Information related to AEs (including concomitant medication taken for ongoing AEs) and new anticancer therapies will be collected. Reasonable efforts should be made to have the patient return for the safety followup visit and report any AEs that may occur during this period. If the patient is scheduled to start a new anticancer therapy before the end of the 30-day follow-up period, the safety follow-up visit should be performed before the new anticancer therapy is started.

7.1.4.2. Disease Follow-up

Patients who discontinue study treatment **for a reason other than disease progression** will move into the disease status follow-up and should be assessed every 8 weeks (\pm 7 days) by radiological imaging to monitor disease status. If the patient discontinues for reasons other than disease progression after 12 months of treatment, then radiographic disease assessments will be performed every 12 weeks (\pm 7 days). Every effort should be made to collect information regarding disease status until:

- Initiation of subsequent anticancer therapy
- Disease progression
- Death
- Withdrawal of consent
- Patient is lost to follow-up
- Defined end of study

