| Physical exam | Х | Х | | Х | Х | | | Х | Х | | See Section 7.3.3 |
| Vital signs | Х | Х | | Х | Х | | | Х | Х | | See Section 7.3.6 |
| Dermatologic exam | X | Х | | | | Х | | X | Х | | Post-treatment follow-up required. See Section 7.3.4. |
| ECOG performance status | X | Х | | Х | Х | | | X | Х | | See Section 7.2.5 |
| Full ophthalmic exam | Х | | Full | ophthalm | ic exams are rec | quired only | v if clinicall | y indicat | ed | | see Section 7.3.5 |
| Visual acuity exam | | Х | | Х | Х | | | | | | see Section 7.3.5 |
| Triplicate 12-lead ECG | X | Х | | | | | | | | | Predose only. See Section 7.3.7 and Table 10 |
| Single 12-lead ECG | | X | | X | | | Х | X | | | C1D1 2.0 h (\pm 0.5 h) after administration of study treatment. See Section 7.3.7 and Table 10 |
| ECHO/MUGA | Х | | | X | | | X | Х | | | See Section 7.3.8 |

Table 3.Schedule of Activities

| Evaluation/ Window | Screening | Treatment Period | | | | Post-Treatment Period | | | Notes/Protocol | | |
|---|------------------|------------------|---|---------------|----------------------|-----------------------|----------------------|--|--|--|--|
| | Screening | Сус | le 1 | Cycle 2 | Subsequent Cycles | Every 8 Weeks | Every 12 Weeks | ЕОТ | Safety Follow-up | Survival Follow- up | Section |
| | Day -28 to -1 | Day 1 | Day 15 | Day 1 ± 3D | Day 1 ± 3D | ± 7D | ± 7D | ± 3D | 30 Days ± 7D | Q12W ± 7D | |
| Tumor radiographic assessment | Х | | | | | Х | | Patient treatme PD will radiog until P criteria | ts who discont ent for reasons Il continue to l raphic assesses D or meet any a in Section 7. | inue s other than have nents Q8W y of the 1.4.2 | Q8W for 12 months then Q12W thereafter. See Sections 7.2.1, 7.2.2 and 7.2.3 |
| Adverse event assessment | Х | | Assess continuously | | | | | | | | See Section 7.5 |
| Laboratory Assessment | s | | | | | | | | | | |
| Hematology | X | Х | | Х | Х | | | Х | X | | See Section 7.3.9 and Table 11 |
| Chemistry | X | Х | | X | Х | | | Х | X | | See Section 7.3.9 and Table 11 |
| Coagulation | Х | P para | Patients on anticoagulation treatment should have parameters monitored throughout the study as clinically indicated | | | | | | | | See Section 7.3.9 and Table 11 |
| Serum pregnancy test | Х | | | | | | | Х | | | See Section 7.3.9.2 and Table 11 |
| Urine pregnancy test | | Perfo | Performed locally on Day 1 of each cycle; or as clinically indicated; or per country-specific requirement | | | | | | | See Section 7.3.9.2 and Table 11 | |

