7.2.3. Tumor Imaging During Treatment

The first imaging assessment should be performed as follows:

- 8 weeks after the first dose of study treatment
- Every 8 weeks (56 days ± 7 days) for 12 months, and then every 12 weeks (± 7 days) thereafter until disease progression is determined or until any of the criteria in Section 7.1.4.2 are met.
- Imaging assessments may be performed more frequently if clinically indicated.

Imaging should follow calendar days and should not be delayed, irrespective of study treatment administration (i.e. delays in cycles or dose holds).

Per RECIST v1.1, responses (PR or CR) should be confirmed by a repeat radiographic assessment. The scan for confirmation of response may be performed no sooner than 4 weeks after the first documented response and no later than the next per-protocol scheduled scan, whichever is clinically indicated.

Radiographic disease assessments should be performed until disease progression per RECIST v1.1, withdrawal of consent, initiation of subsequent anticancer therapy, patient is lost to follow-up, death or defined end of study (see Section 4.5 and Section 6.8).

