4. INVESTIGATIONAL PLAN

4.1. Overall Study Design and Plan

This is an open-label, multicenter, non-randomized, Phase 2 study to determine the safety, tolerability, and efficacy of encorafenib given in combination with binimetinib in treatment-naïve and previously treated participants with *BRAF*^{V600}-mutant metastatic NSCLC. Participants who are either treatment-naïve, or who have received 1) first-line treatment with standard platinum-based chemotherapy, or 2) first-line treatment with an anti-PD-1/PD-L1 inhibitor given alone or in combination with platinum-based chemotherapy will be enrolled. Treatment will be administered in 28-day (\pm 3 days) cycles and will continue until disease progression, unacceptable toxicity, withdrawal of consent, start of subsequent anticancer therapy, or death. Once the participant discontinues study treatment, the treatment period will end, and the participant will enter the follow-up period for safety, subsequent anticancer therapy, disease status, and survival status; participants who discontinue treatment for reasons other than PD will continue to have radiographic assessments every 8 or 12 weeks until PD or subsequent anticancer therapy.

Additional information regarding eligibility criteria, planned dose levels, schedules of assessments, and other study design details and procedures are detailed in the clinical study protocol.

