7.5.5. Progression-free Survival

Progression-free survival is defined as the time from the date of first dose of study drug to the earliest date of disease progression, as determined by IRR and investigator per RECIST v1.1, or death due to any cause, whichever occurs first, and will be summarized in months:

$$\text{PFS (months)} = [(\text{date of event or censoring} - \text{date of first dose}) + 1] / 30.4375.$$

Participants without an event or with an event more than 16 weeks (for the first 12 months after treatment start date) or 24 weeks (after the first 12 months of treatment start date) after the last adequate tumor assessment will be censored on the date of the last adequate tumor assessment that documented no progression. In addition, if a new anticancer therapy is started prior to an event, the participant will be censored on the date of the last adequate tumor assessment that documented no progression prior to the start of the new anticancer therapy. Note: if date of progression occurs on the same date as the start of new anticancer therapy, the progression will be counted as an event.

An adequate post-baseline assessment is defined as an assessment where a response of CR, PR, SD, non-CR/non-PD, or PD can be determined. Time points where the response is NE or no assessment was performed will not be used for determining the censoring date.

Participants with no baseline tumor assessment (including participants with an inadequate baseline assessment) or with no adequate post-baseline tumor assessments within 16 weeks after treatment start date will be censored on the day of treatment start date, unless the participant dies within 16 weeks of treatment start date, in which case, death will be an event on date of death.

The censoring and event date options to be considered for the PFS analysis are presented in Table 4.

Table 4. PFS Outcome and Event Dates

Situation	Date of Progression/Censoring	Outcome
No adequate baseline assessment	Date of treatment start date ^a	Censored ^a
PD or death ≤ 16 (or 24) ^b weeks after last adequate tumor assessment or ≤ 16 weeks after treatment start date	Date of PD or death	Event
PD or death > 16 (or 24) ^b weeks after the last adequate tumor assessment ^c	Date of last adequate tumor assessment ^c documenting no PD prior to new anticancer therapy or missed assessments	Censored
No PD		
New anticancer therapy given		

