^a If the participant dies ≤ 16 weeks after treatment start date, the death is an event with date on death date.

^b Durations are equal to 2 times the length of the tumor assessment interval, which is 16 weeks for the first 12 months after treatment start date, and 24 weeks thereafter.

^c If there are no adequate post-baseline assessments prior to the PD or death, then the time without adequate assessment should be measured from treatment start date; if the criteria is met, the censoring will be on treatment start date.

An estimate of the PFS survival function will be constructed using the KM method (Kaplan & Meier, 1958³) as implemented in PROC LIFETEST. The 25%, median, and 75% DOR (in months) will be summarized along with 95% confidence intervals as calculated from the PROC LIFETEST output (using method of [Brookmeyer & Crowley, 1982¹]).

Frequency counts and percentages of participants with each event type (PD or death) and censoring reasons will be summarized. Censoring reasons are as follows:

- Ongoing in the study without an event
- No adequate baseline assessment
- No adequate post-baseline assessment
- New anticancer therapy was given
- Progression or death after 2 or more missed assessments
- Withdrawal of consent
- Lost to follow-up

If a participant meets multiple definitions for censoring the list below will be used to define the hierarchy.

Table 5. Censoring Reasons and Hierarchy

Hierarchy	Condition	Censoring Reason
1	No adequate baseline assessment	No adequate baseline assessment
2	Start of new anticancer therapy before event.	Start of new anticancer therapy
3	Event after 2 or more missing or inadequate postbaseline tumor assessment	Event after missing or inadequate assessments ^a
4	No event and [withdrawal of consent date \geq , date of first dose OR End of study (EOS) = Participant refused further follow-up]	Withdrawal of consent
5	No event and lost to follow-up in any disposition page	Lost to follow-up
6	No event and [EOS present OR any disposition page after screening says participant will not continue into any subsequent phase of the study] and no adequate postbaseline tumor assessment	No adequate postbaseline tumor assessment
7	No event and none of the conditions in the prior hierarchy are met	Ongoing without an event

a .More than 16 weeks after last adequate tumor assessment.

A graph of the estimated KM curve will be presented.

In addition, time to progression/censoring, event and censoring reasons will be listed.

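### Patients who stop treatment before 12 months without progression have two possible scan schedules after month 12, and the SAP's 24-week gap limit for PFS and DOR fits only one of them (minor)

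*Protocol*

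**What the plan says.** **Protocol 7.1.4.2.** Patients who stop for a reason other than progression "will move into the disease status follow-up and should be assessed every 8 weeks". The interval lengthens in one stated case, a patient who "discontinues for reasons other than disease progression after 12 months of treatment, then radiographic disease assessments will be performed every 12 weeks". Nothing is said about a patient who stops earlier and is still in disease follow-up after month 12.

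**Protocol 7.2.3.** Scans start 8-weekly. Once 12 months have passed the rule is "and then every 12 weeks (± 7 days) thereafter until disease progression is determined or until any of the criteria in Section 7.1.4.2". The criteria it points to are new anticancer therapy, progression, death, withdrawal of consent, loss to follow-up and end of study. Stopping treatment is not among them.

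**Schedule of Activities, imaging row.** The note reads "Q8W for 12 months then Q12W thereafter". The post-treatment cell, for patients who stop without progression, gives Q8W until progression or a 7.1.4.2 criterion. The cell's text is damaged in the copy reviewed, but Q8W is legible.

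**SAP 4.1.** Participants who stop for other reasons than progression "will continue to have radiographic assessments every 8 or 12 weeks until PD or subsequent anticancer therapy", with no rule on who gets which interval.

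**SAP 7.5.5.** A participant "with an event more than 16 weeks (for the first 12 months after treatment start date) or 24 weeks" (from then on) past the last adequate scan is censored at that scan. Table 4 footnote b gives the basis: "Durations are equal to 2 times the length of the tumor assessment interval, which is 16 weeks for the first 12 months after treatment start", and 24 weeks later on. The listed censoring reasons include an event that follows at least two missed scans. Table 5 footnote a gives a single limit of 16 weeks. SAP 7.5.2 applies the PFS censoring rules to DOR.

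**The concern.** Section 7.1.4.2 sets the off-treatment interval by how long the patient was on treatment; 7.2.3 and the Schedule note set it by time elapsed. The two differ for patients who stop before 12 months without progression or new therapy and stay event-free past month 12. A site can follow either and comply with the text.

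The SAP limit goes by time since treatment start and takes 12 weeks as the interval for everyone after month 12. If some patients are in fact scanned 8-weekly, the limit no longer means what footnote b says. Within one cohort, progression would then be looked for on two calendars, and one more missed scan would be tolerated for some patients than for others.

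This falls in a period that matters for describing durability. The protocol's reference medians for dabrafenib plus trametinib in treatment-naïve patients (2.1.2) are 10.9 months for PFS and 10.4 months for DOR. The final treatment-naïve ORR analysis comes 14 months after the last such enrolment (SAP 7.5).

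**Working it through.** **Inputs.** Intervals of 8 and 12 weeks (protocol 7.1.4.2, 7.2.3); limits of 16 and 24 weeks, and the rule limit = 2 × interval (SAP 7.5.5, Table 4 footnote b); 16 weeks alone (Table 5 footnote a). Scan dates are nominal.

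**1. The SAP's own figures.** 2 × 8 = 16 weeks and 2 × 12 = 24 weeks. They reproduce on the 7.2.3 schedule.

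**2. The two calendars.** Twelve months is 365.25 / 7 = 52.2 weeks, so the last 8-weekly scan inside it is week 48. Take a patient who stops at month 6 without progression or new therapy. Scans to week 48 are the same under both sections. After that:
- 7.1.4.2 as written: weeks 56, 64, 72, 80, 88, 96.
- 7.2.3, counting the first 12-week step from week 48: weeks 60, 72, 84, 96.

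**3. The 24-week limit in scan intervals.** 24 / 12 = 2, as footnote b states. 24 / 8 = 3, which it does not.

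**4. Missed scans before an event is censored.** An event found at the k-th scheduled scan after the last adequate one has k − 1 scans missed and a gap of k × interval. It is censored if the gap exceeds the limit.

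| Interval | Limit | 1 missed | 2 missed | 3 missed |
|---|---|---|---|---|
| 8 wk | 16 wk | event (16) | censored (24) | censored (32) |
| 8 wk | 24 wk | event (16) | event (24) | censored (32) |
| 12 wk | 24 wk | event (24) | censored (36) | censored (48) |
| 12 wk | 16 wk | censored (24) | censored (36) | censored (48) |

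Rows 1 and 3 match the SAP's reason of two or more missed scans. Row 2 is the early stopper kept on 8-weekly scans after month 12.

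**5. Example.** Last adequate scan at week 64, weeks 72 and 80 missed, progression at week 88. The gap is 88 − 64 = 24 weeks, not above 24, so it is an event. The same pattern before month 12 (adequate at week 16, weeks 24 and 32 missed, progression at week 40) has a gap of 24 weeks, above 16, and is censored at week 16.

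**6. Table 5 footnote a.** With 12-weekly scans, 16 / 12 = 1.33 intervals (row 4). An event after one missed scan, at 24 weeks, exceeds the Table 5 limit but is an event under Table 4. This concerns anyone scanned 12-weekly after month 12, not only early stoppers.

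**7. Size.** If progression falls evenly between scans, the mean detection lag is 8 / 2 = 4 weeks or 12 / 2 = 6 weeks. The difference is 2 weeks, or 14 / 30.4375 = 0.46 month per patient scanned differently. The documents give no count of such patients. Purely as an assumption, 5–10% of 60 treatment-naïve patients is 3–6, and the shift averaged over the cohort is 0.46 × 3/60 = 0.02 to 0.46 × 6/60 = 0.05 month.

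**The case against.** The best answer is that the passages can be read as one calendar. Section 7.1.4.2 does not say that early stoppers stay on 8-weekly scans after month 12; it is silent. Section 7.2.3 is headed as imaging during treatment, but it runs on to progression or a 7.1.4.2 criterion, so it can supply the missing switch. The Schedule note agrees, and SAP 4.1 is compatible. On that reading, Table 4 is right. This reading is possible, but the text does not compel it: a site that follows 7.1.4.2 and the Q8W in the post-treatment cell also complies.

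Three further objections stand and limit the point.
- A reader might infer that the SAP moves everyone to 12-weekly scans. It does not. It sets censoring limits, and on off-treatment scans it says only 8 or 12 weeks.
- A reader might infer a looser limit for patients off drug. In calendar time it is the same 24 weeks for all after month 12; only the number of scans that may be missed differs.
- A reader might take 3–6 of 60 as the number of changed outcomes. It is an assumed count of patients scanned differently. For event status to change, such a patient must also miss, or have inadequate, two consecutive 8-weekly scans and then have an event more than 16 and at most 24 weeks after the last adequate scan.

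**Conclusion.** The inconsistency is in the current text and is minor. For patients who stop before 12 months without progression or new therapy and are event-free past month 12, the protocol supports two scan schedules. If such a patient is kept on 8-weekly scans, the SAP limit is three intervals rather than the two it claims, and one extra missed scan is tolerated before an event is censored. Separately, Table 5 footnote a contradicts Table 4 after month 12; that does not depend on how 7.1.4.2 is read.

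The documents do not support a claim that PFS or DOR is materially biased. Both are secondary and estimated by Kaplan–Meier without a formal test, the schedules coincide until about month 12, and the size of the affected group is not given. The response rules of 32/60 and 13/37 are untouched. The missed-scan counts rest on nominal dates: with a ±7-day window at each end, a nominal 24-week gap can be 22 to 26 weeks, and one above 24 would be censored on either schedule.

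**What to change.** **Protocol.** Reconcile 7.1.4.2, 7.2.3 and both entries in the Schedule of Activities imaging row, so that one off-treatment imaging schedule applies to patients who stop before 12 months. Which schedule is for the sponsor to decide.

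**SAP.** Make the 7.5.5 text, Table 4 with footnote b, and Table 5 footnote a all use the same limit: twice the patient's scheduled scan interval at that time. DOR follows through 7.5.2.

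**Cost.** Text edits only. The protocol edits can wait for the next amendment, since amendments go to the regulatory authorities before use (9.1). The SAP edits belong in the next SAP version and can be made alone. In that case the SAP must also say how it determines the scheduled interval for early stoppers while the protocol still supports two.
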